Currently, at our institution, TAP or QL blocks are routinely performed for laparoscopic donor nephrectomy based on provider preference. Previous studies regarding quadratus lumborum block have been thoroughly reviewed.^{7-10, 12-13} The principal investigator has previously completed a prospective, randomized clinical trial comparing the efficacy of regional anesthesia techniques for post operative pain management after total knee replacement surgery. The design of the proposed study is comparable to the previously completed study.

D. RESEARCH DESIGN AND METHODS (including data analysis)

This will be a prospective randomized double-blinded trial to compare TAP block versus QL block for pain management in living donor nephrectomy patients. Participants will be blinded to the type of block received and physicians will be blinded both intra- and post-op regarding which block patients received. The team who performs the block will know which block the patient received. No one else involved in the care of the patient will know. The surgery team will not know, and the primary (in the OR) anesthesia team will not know. None of the providers involved in post-operative care of the patient will know.

It is expected that the QL block will provide superior pain control and for a longer duration. Specifically, both groups are expected to show an increase in pain as the block wears off but those who received a TAP block are expected to show an earlier rate of pain increase.

The primary outcome of interest will be patient reported pain on the 10 point NRS scale¹⁴ measured initially in the recovery room (PACU) and then collected at "random" times by the floor nurses up to the first 24 hours post-op. Secondary outcomes will include opiate consumption over time, occurrence of side effects, occurrence of block related issues, PACU length of stay, and hospital length of stay (defined by time to meet discharge criterion).

Patients meeting inclusion criteria will be given a copy of the consent document during their pre-op visit. Consent will be obtained in holding on the day of surgery by an IRB approved, CITI certified study team member that has been trained on the protocol. Participants will be randomized to receive a bilateral TAP block or a bilateral QL block based upon a computerized randomization provided by our statistician.

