After informed written consent, as part of usual clinical care, monitors will be applied and sedation provided at the discretion of the block team. Blocks will be performed under the supervision of a regional anesthesia attending experienced in the performance of both the TAP and QL blocks. Both blocks will be performed using ropivacaine 0.375% 20ml each side for a total volume of 40cc. All patients will receive standard of care pain management.

Inclusion:

Patients undergoing laparoscopic assisted donor nephrectomy

Patients that have elected to have a nerve block

18 years of age or older

Patients of ASA status I – III

Exclusion criteria:

Chronic pain or narcotic usage during the preceding 30 days

Infection at or near the intended needle insertion site

Complex or altered abdominal wall anatomy

Weight <45kg

Members of the research team will collect the following data via review of the electronic medical record:

- Total dose narcotics administered during the intraoperative period in IV morphine equivalents
- Total dose of narcotics administered in the recovery room in IV morphine equivalents
- Total dose of narcotics administered during the first 24 hours following PACU discharge in IV morphine equivalents
- Pain scores
- Date and time of discharge in order determine length of stay

Statistical Analysis:

The primary outcome of this study is NRS pain score over the first 24 hours as described by a linear mixed model which accounts for variability in frequency and number of pain assessments.

The primary outcome of interest is patient reported pain measured on a 10 point NRS scale over the first 24 hours post-op. Comparison of patient reported pain over time between the two block groups will be evaluated using a linear mixed model approach. The model will include fixed effects for block type, post-operative time, and a block by time interaction and a random subject effect to account for repeated measures on the same subject over time.

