Various correlation structures will be considered and the final structure will be selected based on the model Akaike information criterion.¹⁵ We will test the hypothesis that pain measured over time differs between the two groups, specifically testing the hypotheses that the slopes of the lines for pain response over time between the two treatment groups are the same. In a study comparing patient reported pain in living donor nephrectomy, Hutchins et al. (2016) observed a median (IQR [range]) maximum patient reported NRS pain score of 6 (5-9 [0-10]) and a median minimum NRS pain score of 3 (0-4 [0-8]) in living donors who received non-liposomal bupivacaine with a transverse abdominis plane block, which is similar to our control patient population.⁶ A sample size of 24 subjects per group (48 subjects total) provides 87% power to detect a 2 point difference in patient reported pain based on a 2-sided test and significance level $\alpha = 0.05$ assuming at least 3 measures per patients and a within subject covariance having a compound symmetric structure with a standard deviation in pain score of 3 points and within subject correlation of 0.5. We will plan to enroll 52 patients (instead of 48) to account for some patients that may be withdrawn. If the within subject correlation is smaller or we have more than 3 measures on average per subject, we will be able to detect even smaller differences. Additionally, Harrell's rule of thumb states that 10 subjects per covariate are required to avoid overfitting.¹⁶ Thus the linear mixed model will also include up to 3 additional covariates, for example gender or amount of opiate consumed, in order to account for factors known to be associated with patient reported pain. MUSC has approximately 35 living donor nephrectomy patients per year and we anticipate at least 80% (28 of 35) will agree to participate in the study, thus enrollment should be completed within 2 years.

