Secondary outcomes include include opiate consumption over time, occurrence of opioid side effects, occurrence of block related issues, PACU length of stay, and hospital length of stay. Comparisons between the two block groups for cumulative opiate consumption over time will also be evaluated using a linear mixed model approach, similar to what is described for patient reported pain over time. Comparisons between treatment groups for all categorical outcomes will be conducted using a chi-square test or Fisher's exact test when appropriate. Differences between treatment groups for PACU and hospital LOS will be evaluated using a two-sample t-test or Wilcoxon rank sum test when appropriate.

E. PROTECTION OF HUMAN SUBJECTS

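### The primary pain model may adjust for opiate consumption, a post-randomisation secondary outcome; if it does, the block difference in pain level is no longer the randomised total effect of QL versus TAP

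*Combined protocol and SAP*

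**What the plan says.** All of this is in section D, Research Design and Methods, of the combined protocol and SAP.

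- **Base model (Statistical Analysis).** "The model will include fixed effects for block type, post-operative time, and a block by time interaction and a random subject effect". It has no opiate term.
- **Covariates (Statistical Analysis, after the sample size).** "the linear mixed model will also include up to 3 additional covariates, for example gender or amount of opiate consumed". The reason given is a known association with pain. The 10-subjects-per-covariate rule cited there governs how many covariates are allowed, not which ones.
- **Primary test.** The plan describes it as "specifically testing the hypotheses that the slopes of the lines for pain response over time between the two treatment groups are the same".
- **Opiate use as an outcome.** "Secondary outcomes will include opiate consumption over time"; and, in the secondary analyses, "Comparisons between the two block groups for cumulative opiate consumption over time will also be evaluated using a linear mixed model approach".
- **Opiate data collected.** There are three totals: intraoperative, recovery room, and "Total dose of narcotics administered during the first 24 hours following PACU discharge in IV morphine equivalents".
- **Exclusion criterion.** "Chronic pain or narcotic usage during the preceding 30 days".

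The plan does not restrict covariates to variables fixed before randomisation, does not settle the list, and does not say which result stands if models with and without opiate use disagree.

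**The concern.** The same variable has two roles. As a secondary outcome it is something the block may change. As a covariate it would be held constant while the block's effect on pain is estimated. Opioid is given in response to pain and may also lower later pain scores, so it can be a consequence of both the block and the patient's pain.

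Holding it constant asks how pain differs between QL and TAP patients who took the same amount of opioid. Those patients are not comparable by virtue of randomisation. If QL works and patients therefore need less opioid, part of the benefit can be adjusted away. If opioid itself lowers the scores, the adjusted difference can instead exceed the total effect.

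The aim in section A is better pain relief over 24 hours, and the sample size targets a 2-point difference in pain. The level difference is therefore a result readers will look for, even though the named test is on slopes. An open covariate list also allows the choice to be made after results are seen.

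**Working it through.** **1. Can it be a baseline covariate?** No. Every opiate amount to be collected is intraoperative or later, and narcotic use in the preceding 30 days is an exclusion. That the block precedes surgery is inferred from consent in holding and the blinded operating-room team. Recovery-room and ward opioid follows the block in any case.

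**2. Inputs from the plan.** SD 3, within-subject correlation 0.5 (compound symmetry), 3 scores per patient, 24 per group, 2-point difference. Variance of a patient's mean score = 9 × (1 + 2 × 0.5)/3 = 6, so SD = 2.449.

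The plan's power figure of 87% does not come back from these inputs. The standard error is 2.449 × √(2/24) = 0.707, and 2/0.707 − 1.96 = 0.868, which gives 80.7% two-sided. That is a separate matter, and nothing below depends on it.

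**3. Closed form for the level difference.** Let r be the within-arm correlation of mean pain with total opioid, and d the QL reduction in opioid in SD units. Both are assumed; the documents give neither. Adjustment subtracts (within-arm regression slope) × (opioid difference), so

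adjusted benefit = 2 − r × 2.449 × d.

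| r | d | Adjusted benefit |
|---|---|---|
| 0.3 | 0.5 | 2 − 0.367 = 1.63 |
| 0.5 | 0.8 | 2 − 0.980 = 1.02 |
| −0.2 | 0.5 | 2 + 0.245 = 2.24 |
| 0, or d = 0 | – | 2.00 |

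**4. Simulation with dosing that responds to pain.** 200,000 patients per arm; between- and within-patient variance 4.5 each; 3 scores; means 5 (TAP) and 3 (QL); dose = max(0, score − 3 + noise with SD s). The patient's mean score was regressed on block, with and without total dose.

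| s | Opioid effect on next score | r | d | Unadjusted benefit | Adjusted benefit |
|---|---|---|---|---|---|
| 1 | none | 0.89 | 0.73 | 2.00 | 0.39 |
| 5 | none | 0.58 | 0.47 | 1.99 | 1.32 |
| 10 | none | 0.34 | 0.28 | 2.01 | 1.78 |
| 1 | −0.5 per unit | – | – | 1.67 | 0.39 |
| 5 | −0.5 per unit | – | – | 1.69 | 1.34 |
| 10 | −0.5 per unit | −0.09 | 0.27 | 1.70 | 1.75 |
| 20 | −0.5 per unit | −0.46 | 0.14 | 1.72 | 1.93 |

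Repeat runs agreed to within about 0.03. About 16% of simulated QL scores fall below zero. Rounding and clipping scores to 0–10 for the first three rows gives unadjusted 1.75 to 1.78 and adjusted 0.28, 1.22 and 1.60: the same direction, with different sizes.

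**5. A second set of assumptions.** 2,000 trials of 24 per arm with 3 scores; patient-level pain SD 2.12; residual opioid SD 1; QL lowers opioid by 1 unit. Effects are QL minus TAP.

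- Opioid driven by pain, no effect of opioid on pain: −2.0 unadjusted, −0.9 adjusted.
- Opioid lowers pain by 0.5 per unit: −2.0 unadjusted; adjusted −2.5 if dosing ignores the patient's tendency to pain, −1.5 if it follows it.
- No true effect on pain, opioid driven by pain: 0.0 with 5% rejections unadjusted; +1.0 (QL looking worse) with 42% rejections adjusted.

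**6. The slope test.** 300 runs, 24 per arm, 3 to 8 scores at unequal times, s = 1, a constant 2-point benefit and no true slope difference. A per-patient opioid total moved the block-by-time estimate by only 0.02 to 0.08 points per 24 h. In the same runs, with a random intercept, it moved the 12-hour block difference from −2.03 to −0.65 when patient slopes varied (SD 4) and from −1.97 to −0.62 when they did not.

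A time-varying cumulative amount moved the slope by 0.74 only when patient slopes varied and just a random intercept was fitted. With a random slope, which AIC preferred in at least 99% of runs, the shift was 0.03. When patient slopes did not vary it was −0.02 or −0.03. A differently coded cumulative dose did not show the large shift. The 0.74 is not an expected size.

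**The case against.** The strongest reply is that the named hypothesis concerns slopes, and step 6 shows that a per-patient opioid total hardly touches it. That stands, and it limits the point to the level difference. It does not dispose of it, because the aim and the 2-point power target both concern how much pain patients have.

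Second, opiate use is only an example and the base model omits it. Also true: the harm is conditional. But the plan says the model will include further covariates, names this one, and contains no rule that would keep it out.

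Third, every size above is assumed. The fall to 0.39 needs a correlation of 0.89, because dose is generated almost directly from the scores being analysed. This stands as well, and none of the figures is a forecast.

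Fourth, pain at equal opioid use is an intelligible clinical question, since rescue opioid affects scores. It is a different question from the randomised comparison, the plan does not declare it as the target, and post-block opioid cannot confound a randomised contrast. It is a reason to read pain and opioid results together.

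**Conclusion.** The concern holds: the covariate sentence is wrong as written and should be fixed. If opiate consumption enters the primary model, the block difference in pain level no longer estimates the total effect of QL versus TAP and may be biased. The two coincide numerically only in special cases, such as opioid unrelated to pain within arm or unaffected by the block.

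Direction and size cannot be determined from the documents. The estimate moves towards zero if opioid use marks greater pain, and away from zero if the within-arm correlation is negative. No bias in the slope test is claimed. The conclusion that the covariate is unsuitable rests on the plan's own text: it is a post-randomisation variable that the plan itself analyses as an outcome. Only the illustrative sizes rest on assumed correlations and dosing behaviour.

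**What to change.** Delete opiate consumption from the example covariates of the primary pain model. State that adjustment is limited to pre-randomisation variables, and name them before outcome data are examined. Gender is already mentioned; age, height and weight are also collected (section E.1.b), but the documents do not say that these relate to pain, so any chosen should have a stated reason. Keep opiate consumption as a secondary outcome, and label any opiate-adjusted or joint pain-opioid analysis as sensitivity only.

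The cost is one sentence of wording. No new data are needed and the sample size does not change.

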1. RISKS TO THE SUBJECTS

a. Human Subjects Involvement and Characteristics

There will be a total of 52 adult (18 years or older) human subject candidates that have undergone an extensive evaluation process to become a candidate for organ donation. Donor nephrectomy candidates are typically healthy volunteers. Volunteers must have an ASA status I – III. Race, ethnicity, and gender will not be considered in subject selection. Special populations including children and other vulnerable patients will not be included in this study. There are no collaborating sites; this is a single center trial.

Targeted/Planned Enrollment Table

Total Planned Enrollment 52

TARGETED/PLANNED ENROLLMENT: Number of Subjects			
Ethnic Category	Sex/Gender		
	Females	Males	Total
Hispanic or Latino			
Not Hispanic or Latino			
Ethnic Category: Total of All Subjects*			
Racial Categories			
American Indian/Alaska Native			
Asian			
Native Hawaiian or Other Pacific Islander			
Black or African American			
White			
Racial Categories: Total of All Subjects*	26	26	

**The "Ethnic Category: Total of All Subjects" must be equal to the "Racial Categories: Total of All Subjects".*

Inclusion criteria include all patients of age 18 years or older, ASA class less than or equal to III, presenting for living laparoscopic donor nephrectomy at MUSC and consenting to participation in the study. Children will not be included in this study. No special classes of subjects will be involved in this study. Race, gender, and ethnicity will not be considered during subject selection. The estimated numbers of participants from ethnic groups, racial groups, and gender groups provided above are based solely on the demographics of the state of South Carolina. These are rough estimates. This study is a single institution study.

b. Sources of Materials

For each subject included in the study, MRN, age, gender, height, and weight, pain scores, medication administration, and length of stay will be collected. Adverse events will be documented and reported to the IRB and the Department of Anesthesia's DSMB per MUSC policy. All participants will be given a numeric identifier that will be used to identify subjects throughout the study. An electronic enrollment log will be kept on a password protected MUSC server and only trained, IRB approved study team members will have access to this information.

c. Potential Risks

There is no increase of medical risk as patients receive nerve blocks during routine care for this surgery. Baseline risks of the intervention include bleeding, infection, damage to surrounding structures, nerve damage, and failed block. The risks for the two interventions are similar.

The alternative is to not participate in the study and the patient will receive the nerve block their provider prefers.

There is a risk of loss of confidentiality.

2. ADEQUACY OF PROTECTION AGAINST RISKS

a. Recruitment and Informed Consent

Potential participants will be given a copy of the consent document during their pre-operative visit. Patients will be given a chance to ask any necessary questions prior to surgery on the same day during their anesthesia workup, as customary for anesthesia. Once a potential participant agrees to volunteer in the study a trained, IRB-approved member of the research team will obtain written consent and a signed HIPPA document. Patients will be given copies of both documents for their records. Children will not be included in this study.

b. Protection against Risk

Any adverse events related to placement of nerve blocks will be treated according to MUSC Hospital policy and procedures and the practice of the Department of Anesthesia.

The Department of Anesthesia's DSMB will review the study on an annual basis. Any adverse events will be reported and reviewed by the DSMB. Adverse events will be reported to MUSC's IRB per policy.

All data will be kept in a locked office, in a locked cabinet, and electronic data will be stored on a password protected MUSC server. Only CITI-certified, IRB approved study team members will have access to data.

3. POTENTIAL BENEFITS OF THE PROPOSED RESEARCH TO THE SUBJECTS AND OTHERS

This study aims to determine whether newer regional anesthesia techniques are superior to current standard practice. The study may result in improved pain control for the subject, and eventually other kidney donors in the future. Other studies in other patient populations have reported improved pain control with lower blood concentration levels of local anesthetic.^{9,10,13} It is reasonable to anticipate that similar results would be demonstrated in this patient population. The risks to the subject are reasonable to the extent that the patients will undergo standard anesthetic management for laparoscopic donor nephrectomy at our institution.

4. IMPORTANCE OF THE KNOWLEDGE TO BE GAINED

Renal failure is a widespread condition throughout the community. A limited supply of organs is available for transplantation, however. Living donation represents a large area to increase the available supply of transplantable kidneys. For many potential donors fear of pain is often a limiting factor in volunteer decisions to donate. By potentially improving postoperative analgesia, more volunteers may be encouraged to consider living kidney donation.¹¹

5. SUBJECT SAFETY AND MINIMIZING RISKS (Data and Safety Monitoring Plan)

Any adverse events related to placement of nerve blocks will be treated according to MUSC Hospital policy and procedures and the practice of the Department of Anesthesia.

Nerve blocks will be performed in the customary fashion in order to minimize the risks of adverse outcomes. Patients will be monitored by the anesthesia care team for adverse events. The anesthesia team is skilled in the management related to the placement of nerve blocks.

The study will be reviewed annually by the Department of Anesthesia's DSMB.

Adverse events will be recorded and reported to the Department of Anesthesia's Data Safety Monitoring Board and the IRB per policy. PHI will be managed in a manner that complies with institutional rules and regulations.

*Clinical Trials

A clinical trial is a prospective biomedical or behavioral research study of human subjects that is designed to answer specific questions about biomedical or behavioral interventions (drugs, treatments, devices, or new ways of using known drugs, treatments, or devices).

Clinical trials are used to determine whether new biomedical or behavioral interventions are safe, efficacious, and effective. Behavioral human subjects research involving an intervention to modify behavior (diet, physical activity, cognitive therapy, etc.) fits these criteria of a clinical trial. Human subjects research to develop or evaluate clinical laboratory tests (e.g. imaging or molecular diagnostic tests) might be considered to be a clinical trial if the test will be used for medical decision-making for the subject or the test itself imposes more than minimal risk for subjects.

F. REFERENCES/LITERATURE CITATIONS

